## **6.8. Prior and Concomitant Therapy**

Any medication or vaccine (including over-the-counter or prescription medicines, vitamins, and/or herbal supplements) that the subject is receiving at the time of enrollment or receives during the study must be recorded along with:

- reason for use
- dates of administration including start and end dates
- dosage information including route, dose, and frequency.

Concomitant medications should be used in alignment with the approved label in the respective country, and per doses as outlined below.

The medical monitor should be contacted if there are any questions regarding concomitant or prior therapy.

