### **6.8.2. Concomitant Therapies**

Upon initiation or discontinuation of investigational product, investigators should consider potential effects on metabolism of cytochrome P450 substrates with narrow therapeutic indices including, but not limited to, methotrexate, tacrolimus, cyclosporine, certain tricyclic antidepressants (including amitriptyline and nortriptyline), baricitinib, warfarin, and tamoxifen. The concomitant medications/treatments in the following sections are permitted during the study.

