### Phase 2 Liver Chemistry Stopping Criteria and Follow-up Assessments

Liver Chemistry Stopping Criteria	
ALT or AST-absolute	ALT or AST $\geq 5 \times$ ULN
ALT or AST Increase	ALT or AST $\geq 3 \times$ ULN persists for $\geq 4$ weeks
Bilirubina,b	ALT or AST $\geq 3 \times$ ULN and total bilirubin $\geq 2 \times$ ULN ( $> 35\%$ direct bilirubin)
International Normalized Ratio (INR)b	ALT or AST $\geq 3 \times$ ULN and INR $> 1.5$
Cannot Monitor	ALT or AST $\geq 3 \times$ ULN and cannot be monitored twice weekly for 4 weeks
Symptomaticc	ALT or AST $\geq 3 \times$ ULN associated with symptoms (new or worsening) believed to be related to liver injury or hypersensitivity
Suggested Actions, Monitoring, and Follow-up Assessments	
Actions	

 
• Immediately discontinue study drug.
 
• Report the event to the sponsor/designee within 24 hours.
 
• Complete an SAE eCRF if the event met the criteria for an SAE.b
 
• Perform follow-up assessments as described in the Follow-up Assessment column.
 
• Monitor the subject until liver chemistry test abnormalities resolve, stabilize, or return to baseline.
 
	
 
• Viral hepatitis serology.c
 
• Obtain blood samples for PK analysis after the most recent dose.d
 
• Obtain serum creatine phosphokinase, lactate dehydrogenase, gamma glutamyl transferase, glutamate dehydrogenase, and serum albumin.
 
• Fractionate bilirubin if total bilirubin <math>\geq 2 \times</math> ULN.
 
• Obtain complete blood count with differential to assess eosinophilia.
 

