---	---

	

○ In subjects with acute or chronic atypical presentation.

● If liver biopsy conducted provides biopsy information.

--	---

Abbreviation: ALT = alanine transaminase; AST = aspartate transaminase; eCRF = electronic case report form; PK = pharmacokinetic; SAE = serious adverse event; ULN = upper limit of normal.

a Serum bilirubin fractionation should be performed if testing is available. If serum bilirubin fractionation testing is unavailable, **record the absence/presence of detectable urinary bilirubin on dipstick** which is indicative of direct bilirubin elevations suggesting liver injury.

b All events of ALT or AST  $\geq 3 \times$  ULN **and** total bilirubin  $\geq 2 \times$  ULN ( $> 35\%$  direct bilirubin) or ALT or AST  $\geq 3 \times$  ULN **and** INR  $> 1.5$  may indicate severe liver injury (**possible “Hy’s Law”**) **and must be reported to sponsor in an expedited manner and as an SAE.** The INR stated threshold value will not apply to subjects receiving anticoagulants.

c New or worsening symptoms believed to be related to liver injury (such as fatigue, nausea, vomiting, right upper quadrant pain or tenderness, or jaundice) or hypersensitivity (such as fever, rash, or eosinophilia).

d Record the date/time of the PK blood sample draw and the date/time of the last dose of study drug prior to the blood sample draw on the eCRF. If the date/time of the last dose is unclear, provide the subject’s best approximation. If the date/time of the last dose cannot be approximated OR a PK sample cannot be collected in the time period indicated above, do not obtain a PK sample. Instructions for sample handling and shipping are in the Study Laboratory Manual.

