6.10.3.1 Liver Function Tests

Subjects who met any (1 or more) of the following liver function test (LFT) criteria at any point after starting study treatment and prior to Week 16 will be included in consideration of potential drug-induced liver injury (DILI) in Period 1:

- Alanine Transaminase (ALT) or Aspartate Transferase (AST) $\geq 5 \times$ upper limit of normal (ULN) at any time
- ALT or AST $\geq 3 \times$ ULN at all (2 or more) assessments in a span of ≥ 4 weeks
- ALT or AST $\geq 3 \times$ ULN and total bilirubin $\geq 2 \times$ ULN ($>35\%$ direct bilirubin) simultaneously at any time
- ALT or AST $\geq 3 \times$ ULN and international normalized ratio (INR) ≥ 1.5 simultaneously at any time
- ALT or AST $\geq 3 \times$ ULN at any time during the study and weekly assessments after this finding are not available for at least 4 weeks
- ALT or AST $\geq 3 \times$ ULN associated with symptoms (new or worsening) believed to be related to liver injury or hypersensitivity at any time

To determine subjects who meet the last criterion, a listing of all subjects who have at least 1 ALT or AST $\geq 3 \times$ ULN at any time after starting study treatment and prior to Week 16, and who do not meet any of the first 5 criteria, will be reviewed by ACELYRIN pharmacovigilance and clinical development representatives along with a listing of all AEs reported by such subjects. In consideration of the investigator's causality assessment, the medical professionals will assess whether any AE is believed to be related to liver injury or hypersensitivity and, if so, whether the elevated ALT or AST is in temporal association with the AE. Any subjects who meet these criteria will be included on a memo that is finalized prior to database lock and that will be filed in the trial master file (TMF).

If there is crossover between Period 1 and Period 2 in any of the instances listed above that require several events over a particular time-span, the LFT flag will be assigned to the period in which the first finding occurs.

Hy's Law is met when all 3 of the following criteria is met simultaneously (at the same draw):

- ALT or AST is $\geq 3 \times$ ULN
- Total bilirubin $\geq 2 \times$ ULN

- Alkaline Phosphatase (ALP) is <2 x ULN

At each assessment through Week 16, subjects will be classified as meeting Hy's Law or not meeting Hy's Law.

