An analogous approach will be used for evaluating Period 2 for potential DILI. Visits after Week 16 will be considered. Only subjects who took at least one dose of treatment in Period 2 are evaluated for Period 2 potential DILI.

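### The SAP's potential-DILI rules for INR and for unmonitored subjects differ from protocol 10.5, and its symptomatic row can be under-counted

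*SAP*

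**What the plan says.** SAP 6.10.3.1 lists six liver criteria; meeting any one places a subject under consideration for potential DILI. All but the first start from, or build on, ALT or AST of at least 3×ULN. Three matter here.

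- Criterion 4 adds an "international normalized ratio (INR) ≥ 1.5 simultaneously at any time". No subject is exempt.
- Criterion 5 applies when "weekly assessments after this finding are not available for at least 4 weeks".
- Criterion 6 is the symptomatic one. It is settled by medical review: a listing of subjects with at least one such elevation and "who do not meet any of the first 5 criteria, will be reviewed by" sponsor pharmacovigilance and clinical staff.

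For the later part of the study, "An analogous approach will be used for evaluating Period 2 for potential DILI".

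SAP 9.8.3.1 then tabulates each of the six criteria separately, through Week 16, through Week 52 and for Period 2 alone. It also lists the affected subjects with the particular criterion each one met, and says that the criteria are the protocol's.

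Protocol 10.5 sets the INR limit strictly above 1.5. Footnote b to its table adds: "The INR stated threshold value will not apply to subjects receiving anticoagulants". Its monitoring criterion applies to a subject who "cannot be monitored twice weekly for 4 weeks". Its symptomatic criterion carries no condition about the other five.

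**The concern.** The SAP claims the protocol's criteria but changes two of them, and SAP section 5, which records departures from the protocol, mentions neither. The symptomatic criterion keeps the protocol's meaning but is assessed in a restricted group, which does not fit a table that gives every criterion its own count.

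The abbreviated report drops other laboratory summaries and listings (SAP 6.10.3 and 9.8.3), so this table and listing are the only clinical safety laboratory output that remains. The INR row also has a specific meaning: under footnote b of protocol 10.5, the protocol's combination of raised transaminase and INR may indicate severe liver injury and must be reported as an SAE. A subject flagged only by the SAP's looser rule could therefore appear in that row with no matching SAE. Because the listing prints the criterion met, a wrong flag carries into it.

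**Working it through.** The plan gives no figure to reproduce. The check sets the two rule sets side by side and runs boundary cases through both.

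| Row | SAP 6.10.3.1 | Protocol 10.5 |
|---|---|---|
| 4, INR | 1.5 or more, everyone | above 1.5, anticoagulant users exempt |
| 5, monitoring | weekly | twice weekly |
| 6, symptoms | looked for only if rows 1–5 are all negative | no precondition |

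**INR boundary** (ALT/AST at least 3×ULN, no anticoagulant). INR 1.4: neither rule flags. INR 1.5: SAP yes, protocol no. INR 1.6: both flag. The monitoring section of protocol 10.5 confirms the boundary, because it puts INR of 1.5 or less, with bilirubin below 2×ULN, in the lower tier.

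**Could anticoagulant users be enrolled?** Protocol 6.8.2 ends its list of drugs to consider with "baricitinib, warfarin, and tamoxifen". Warfarin is not on the prohibited list in protocol 6.8.3, and protocol 10.5 provides for such subjects. How many there are is unknown.

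**Six illustrative profiles.** Each assumes a single elevation lasting under 4 weeks with adequate monitoring, so rows 2 and 5 are not met.

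| Profile | SAP rows | Protocol rows |
|---|---|---|
| A: ALT 3.4×ULN, INR 1.5 | 4 | none |
| B: ALT 3.4×ULN, INR 2.4 on anticoagulant | 4 | none |
| C: ALT 6×ULN, symptoms | 1 | 1, 6 |
| D: ALT 3.4×ULN, INR 2.4 on anticoagulant, symptoms | 4 | 6 |
| E: ALT 3.4×ULN, INR 1.6, no anticoagulant | 4 | 4 |
| F: ALT 3.4×ULN, symptoms only | 6 | 6 |

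Whether the subject meets any criterion changes in A and B. Only the rows change in C and D. E and F agree. In D the mistaken INR flag also removes the subject from symptom review.

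**Row 5.** Take n draws spread evenly over the 4 weeks after the finding. Twice weekly needs n ≥ 8. If the SAP means a draw in every week, it needs n ≥ 4, so the rules differ at n = 4 to 7; 0 to 3 draws fail both and 8 or more satisfy both. If the SAP means no draw at all in 4 weeks, it flags only n = 0 and the rules differ at n = 1 to 7. Scheduled chemistry, as the Schedule of Activities was extracted, falls at Weeks 4, 8, 12 and 16. On the first reading, a subject with scheduled draws only is flagged under both rules, and the SAP then leaves that subject out of symptom review.

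**Size.** One subject is 1/125 = 0.8 percentage points of a planned arm, or 1/250 = 0.4 overall. An error in Period 1 enters the Week 16 and Week 52 tables; one in Period 2, for a subject dosed then, enters the Week 52 and Period 2 tables. Either way it appears in two of the three.

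**The case against.** The strongest reply is that the two documents serve different purposes. Protocol 10.5 governs stopping and reporting for individual subjects, whereas the SAP builds a screening table that the protocol's safety analysis section (9.3.5) does not call for. A wider screen is defensible, the INR differences can only over-include, and the listing shows the INR value. Eligible pairs are probably few, since the extracted schedule has no coagulation row and INR is named chiefly in the repeat liver work-up. The warfarin mention is weak evidence, because the same sentence names drugs that the protocol prohibits.

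On row 5, the protocol's wording is a judgement of feasibility, so some data-based proxy is needed. Protocol 10.5 also lets lower-tier monitoring fall to weekly or less once values settle or study drug stops, so a flat twice-weekly rule would flag correctly managed subjects. Row 6 can be read as a residual category. Subjects already captured have all their liver results and AEs listed, and Hy's Law is counted separately without INR.

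Most of this stands as an argument about weight. It does not remove the mismatch: SAP 9.8.3.1 says the listing follows the protocol, and row 6 is not labelled as residual. The row 5 point does limit the remedy there.

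**Conclusion.** The concern holds as a minor point. Followed exactly, the SAP over-counts row 4 for a subject with INR of exactly 1.5, or with an INR raised by an anticoagulant, and under-counts row 6 for a symptomatic subject who meets another criterion. Row 5 uses a different frequency, and the error there can go either way, given the protocol's allowance for reduced monitoring.

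The symptom-review restriction leaves the any-criterion total unchanged, because an omitted subject already meets one of the first five criteria. The INR differences can raise that total. The row 5 difference can change it for a subject who meets nothing else.

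The 0.8-point figure rests on 125 per arm; the Period 2 table uses only subjects dosed in that period, so one subject there weighs at least as much. The profiles are illustrative and say nothing about frequency. The reading of the INR and symptomatic rows is secure; the draw counts for row 5 depend on even spacing and on how the SAP phrase is read. Safety data carry no p-values (protocol 9.3.5), and efficacy, site stopping actions and the AE/SAE listings are unaffected. Laboratory data remain in the analysis datasets.

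**What to change.** 1. Set SAP criterion 4 to INR above 1.5 and exempt subjects receiving an anticoagulant at the time. The data exist: under protocol 6.8, any medication "that the subject is receiving at the time of enrollment or receives during the study must be recorded along with" its reason, dates and dose.
2. Review every subject with ALT or AST of at least 3×ULN for symptoms, so that row 6 is a true count.
3. For criterion 5, choose one of two courses. Either require twice-weekly assessments for the period in which protocol 10.5 still demands them, or state that weekly availability is a deliberate data-based proxy, define what counts as unavailable, and drop the claim that this row follows the protocol.
4. Apply the same rules to Period 2 and record any retained departure in SAP section 5.

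The cost is SAP wording, one re-derived INR flag with a concomitant-medication check, and a somewhat longer list for a medical review already required before database lock. The twice-weekly option also needs someone to judge when values have resolved or stabilised; the proxy avoids that. No new data are needed.

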6.10.4 Electrocardiograms (ECGs)

TriPLICATE 12-lead ECGs will be obtained after subject has been supine for at least 5 minutes using an ECG machine that automatically calculates the heart rate and measures PR, QRS, and QT intervals. The overall interpretation of findings, any abnormal findings, and the clinical significance status are collected on the eCRF.

ECG results will not be listed, but will be available in the analysis datasets.

6.10.5 Vital Signs

The change from baseline at each visit through Week 52 will be calculated as: *the current visit value minus the baseline value*, for the following vital sign parameters:

- SBP (mmHg)
- DBP (mmHg)
- Heart Rate (bpm)
- Respiration Rate (breaths/minute)
- Body Temperature (C) – temperatures collected in Fahrenheit will be converted to C using the following formula: *(temperature in Fahrenheit – 32) x 5/9*

6.10.6 Physical Examination

Clinically significant findings observed prior to the first dose of study drug will be entered on the CRF in medical history in the CRF and reported as medical history. Clinically significant findings observed after the first dose of study drug will be reported as AEs in the CRF and reported as AEs.

Physical examination results will not be listed, but will be available in the analysis datasets..

7. ANALYSIS SETS

The analysis sets are defined in [Table 6](#) below:

Table 6: Analysis Sets

Analysis Set	Definition	Used for Analyses
All Screened Set	All subjects who signed the informed consent form.	Study Disposition
Full Analysis Set (FAS)	All subjects who were randomized. Subjects will be analyzed based on their planned treatment.	Treatment Disposition, Baseline, Protocol Deviations, Efficacy
Full Analysis Set P2 (FASP2)	All subjects who were randomized and took at least one dose of treatment in Period 2.	Efficacy analyses of "Period 2 only".

Analysis Set	Definition	Used for Analyses
	Subjects will be analyzed based on their planned/randomized treatment course.	
Safety Analysis Set (SAF)	All subjects who were randomized and received at least 1 administration of study treatment. Subjects will be analyzed based on the actual treatment received. If a subject receives both treatments, the subject will be grouped with the treatment received most often.	All safety analyses, PK, ADA analyses.
Safety Analysis Set P2 (SAFP2)	All subjects who were randomized and received at least 1 administration of study treatment in Period 2 of the study. Subjects will be analyzed based on the actual treatment course received (Placebo QW – Izokibep 160 mg QW or Izokibep 160 mg QW). If a subject receives both treatments in Period 1, the subject will be grouped with the treatment received most often.	Safety analyses of “Period 2”.

8. STATISTICAL METHODS

8.1 General Methodology

Unless otherwise specified, all hypothesis tests will be reported with 2-sided p-values. All confidence intervals (CIs) will be 2-sided with nominal 95% coverage. An adjustment of 0.0001 will be made to account for the unblinded data summaries reviewed by the Independent Data Monitoring Committee (IDMC). Hypotheses testing will be adjusted to control the error rate in the strong sense at $\alpha = 0.0499$. The hypotheses will therefore be tested at $\alpha = 0.0499$.

All data summaries after Week 16 are considered exploratory.

For binary efficacy endpoints, stratified tests will use the 4 strata from the randomization process. If a subject was incorrectly classified during the randomization process, the analysis will use the correct classification as recorded in EDC, not the classification used during randomization.

Tabulations will be produced for demographic, baseline, limited efficacy, and relevant safety parameters. For categorical variables, summary tabulations of the number (n) and percentage (%) of subjects with non-missing data per category will be the default summary presentation, and where appropriate and present, the number of missing values as a “Missing” category. For continuous variables, the number of subjects (n), mean, standard deviation (SD), median, minimum, and maximum will be presented. Coefficient of variation (%CV) may be presented for certain analyses. The number of subjects in the analysis population will be used as denominator for percentages calculation, unless stated otherwise in TFLs mock shell(s).

The treatment group labels, and presentation order are as follows:

- Placebo QW – Izokibep 160 mg QW
- Izokibep 160 mg QW

8.2 Adjustments for Covariates

Each instance of mixed model repeated measures (MMRM) will use the observed baseline of the parameter used in the response variable as well as stratification as covariates.

8.3 Handling of Dropouts or Missing Data

When considering AE and Concomitant Medications, partial start/end dates will be handled in a conservative fashion so that if there is any possibility that the available partial information could reasonably result in the AE being treatment-emergent or the medication being concomitant, that it will be imputed as such. Specifically:

- If the start day is missing but month and year are present:
 - o If the known month/year are the same as the month/year of the first dose of treatment, then impute to the date of the first dose of treatment;
 - o Otherwise, impute the day to 01.
- If the start day and month are both missing but the start year is present:
 - o If the known year is the same as the year of the first dose of treatment, then impute to the date of the first dose of treatment;
 - o Otherwise, impute the day and month to 01January.
- If the start date is completely missing, impute to the date of the first dose of treatment, unless the end date suggests it could have started prior to this, in which case impute to 01January of the same year as the end date.
- When imputing a start date, ensure that the new imputed date is on or prior to the end date of the AE or medication.
- If the end date is missing or partial, and the AE/medication is not ongoing (i.e. for AE, the outcome is not “Recovering/Resolving”, “Not Recovered/Not Resolved”, or “Unknown”), then impute the missing/partial end date as follows:
 - o If the end day is missing but month and year are present:
 - If the known month/year are the same as the month/year of the first dose of treatment, then impute to the date of the first dose of treatment;
 - Otherwise, impute the day to the last day of the month.
 - o If the end day and month are both missing but the end year is present:
 - If the known year is the same as the year of the first dose of treatment, then impute to the date of the first dose of treatment;
 - Otherwise, impute the day and month to 31December.
 - o If the end date is completely missing, impute to the date of the first dose of treatment.
 - o When imputing an end date, ensure that the new imputed date is on or after the start date of the AE or medication.
- Other unexpected combinations of partial date information (e.g., known month but missing day and year) will be handled as needed on a case-by-case basis.

The handling of missing efficacy data will be discussed throughout sections 6 and 9.

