## 4. Study Design

### 4.1. Overall Design

This is a Phase 3, pivotal, confirmatory, randomized, double-blind, placebo-controlled, parallel-group study to evaluate the efficacy and safety of izokibep in subjects with moderate to severe HS. Subjects must have HS lesions present in  $\geq 2$  distinct anatomic areas, one of which must be Hurley Stage II or Hurley Stage III, and a total AN count of  $\geq 5$ . Subjects with draining fistula count of  $> 20$  at screening or Day 1 will be excluded.

Overall, 250 subjects (125 subjects per treatment group) with moderate to severe HS are planned to be enrolled at sites globally in North America, Europe, and Asia Pacific. Additional sites and regions may be added.

Subjects meeting eligibility criteria will be randomized into 1 of 2 treatment groups in a 1:1 ratio as follows:

- Group 1 (n = 125): placebo QW from Day 1/Week 0 through Week 15, then izokibep 160 mg QW from Weeks 16 to 51.
- Group 2 (n = 125): izokibep 160 mg QW from Day 1/Week 0 through Week 51.

The first dose of study drug (ie, izokibep or placebo) will be administered on Day 1 (Week 0).

Randomization will be stratified by prior TNFi use for HS (Yes/No) and Hurley Stage (II or III). The AN count is the sum of abscesses and inflammatory nodules. Subjects enrolled with stable concomitant antibiotic use (dosing regimen has been stable for  $\geq 4$  weeks prior to first dose of study drug) will be capped at approximately 30%.

Subjects will complete study assessments according to the study visits outlined in the schedule of activities (SoA) ([Section 1.3](#)). The primary endpoint will be assessed at Week 12. The last dose of study drug will be administered on Week 51.

An end of treatment visit will be conducted at Week 52 ( $\pm 5$  days). A safety follow-up visit will be conducted at Week 59 ( $\pm 5$  days). For subjects who early terminate, the end of treatment visit should be completed 1 week after last dose of study drug ( $\pm 5$  days), and safety follow-up visit should be completed 8 weeks after last dose of study drug ( $\pm 5$  days), where possible.

The final analysis of primary and secondary endpoints will be conducted after the last subject has had the opportunity to complete Week 12 assessments or early terminates from the study.

Analysis of data at later timepoints may occur after all subjects have had the opportunity to complete that timepoint.

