6.10.2 Adverse Events

All AEs recorded on the CRF will be coded using the latest MedDRA dictionary around the time of Database Lock and classified as either AEs or TEAEs as follows:

- TEAEs in Period 1 are defined as:
 - Any adverse event with a start date/time after the first administration of study drug in the Treatment Period until the date/time of the Week 16 dose administration.
 - If the subject discontinued study treatment prior to taking the Week 16 dose, then 28 days from last dose of study drug administration will be used as the upper limit of the time-period, or
 - If a subject does not have treatment discontinuation prior to Week 16 dose and is missing the Week 16 dose and all subsequent doses, then the study day 112 will be used as the upper limit of the time-period, or
 - In the case of the subject missing Week 16 dose and continuing treatment in the study, the date/time of the first dose of drug in Period 2 will be used as the upper limit of the time-period
 -
 -
- TEAEs in Period 2
 - Events with start date and time after the start of administration of Period 2 treatment and up to 4 weeks after the end of the Treatment Period, or events with start date and time prior to the start of administration of Period 2 treatment whose severity worsens on or after the start of administration of Period 2 treatment and up to 4 weeks after the last dose of study treatment.
 - For subjects who receive treatment in period 2, TEAEs with start date after the start of period 2 will be assigned to period 2 only, not to period 1
- Treatment-emergent SAE are TEAEs that are indicated as Serious = "Yes".

- The relationship between a TEAE and treatment is assessed as related or not related. Treatment-related TEAEs are TEAEs that are indicated as “related to treatment”. If relationship to treatment is missing or unknown, then the TEAE is considered “related to treatment”.
- TEAEs leading to discontinuation of treatment are TEAEs where the “Action Taken with study treatment” = “Drug Withdrawn”
- Assessment of AE severity will be based on CRF AEs form. TEAEs with missing severity will be included in the counts as severe (Grade 3) unless the TEAE has an outcome of fatal; in that case, the TEAE with missing severity will be included in the counts as death (Grade 5).

6.10.2.1 *Injection Site Reaction*

Injection Site Reaction (ISR) is defined as

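### SAP 8.3 has no start-date rule for the month of the first Period 2 dose, so in placebo-first subjects an AE with an unknown start day in that month is nearly always counted under placebo

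*SAP*

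**What the plan says.** SAP 8.3 gives one set of rules for incomplete AE and medication dates, introduced by the statement that "partial start/end dates will be handled in a conservative fashion". For a start with known month and year but no day, the date of the first dose is used in one case only: "If the known month/year are the same as the month/year of the first dose of treatment". In every other month the rule is "Otherwise, impute the day to 01". The first Period 2 dose is not mentioned.

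SAP 6.10.2 assigns AEs to periods. Period 1 runs from the first dose "until the date/time of the Week 16 dose administration". Period 2 takes "Events with start date and time after the start of administration of Period 2 treatment", plus earlier events "whose severity worsens on or after the start of administration of Period 2 treatment". It adds that for subjects treated in Period 2, "TEAEs with start date after the start of period 2 will be assigned to period 2 only".

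Protocol 4.1 gives Group 1 placebo through Week 15, "then izokibep 160 mg QW from Weeks 16 to 51". SAP 9.8.2 tabulates AEs by treatment group through Week 16, again for Period 2, and for the two periods combined.

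**The concern.** For a placebo-first subject the Period 1/Period 2 boundary is also the boundary between placebo and izokibep. A date rule that knows only the first dose cannot respect it. If the site records only the month of onset, and that month contains the switch, the rule places the onset at the start of the month. An event that may have begun after the first izokibep dose is then reported in the placebo column of the Period 1 tables and is absent from the Period 2 izokibep column, unless it worsens in Period 2. What is at stake is treatment attribution in the period-specific AE tables. No section of either document says how a partially dated AE is to be assigned to a period.

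**Working it through.** The plan states no figure on this point, so there is none to reproduce. The check applies the SAP 8.3 rule and the SAP 6.10.2 limits to calendar dates.

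**Inputs**
- Week 16 dose W = first dose + 112 days. SAP 6.10.1 uses 112 days for Period 1, and SAP 6.2.2 schedules Week 16 at day 112.
- Dosing window ±3 days (Protocol 1.3), so +109 and +115 were also tried.
- Imputed start = day 01 of the month of W, if that is not the first-dose month.
- Period 1 if the imputed start is before W.
- First-dose dates: every date in a four-year calendar, 1 January 2023 to 31 December 2026, which is 1461 dates. The calendar is an assumption; the result hardly depends on it.

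**Step 1: does the first-dose branch ever apply in the crossover month?** No. The shortest gap, 109 days, exceeds any month. W fell in the first-dose month for 0 of 1461 dates at each of +109, +112 and +115. The day-01 branch therefore always governs.

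**Step 2: where does day 01 fall relative to W?** It equals W only when W is the first of a month. Four years contain 48 such dates: 48/1461 = 3.3%. For these the imputed start has no time of day, so the period is undefined. In the other 1461 − 48 = 1413 dates (96.7%), day 01 precedes W and the AE goes to Period 1. The counts are the same at all three offsets.

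**Step 3: how much of the crossover month is after the switch?** For a month of L days with W on day w (w = 2 to L), L − w + 1 days are on or after W. Averaged over w, the share is [L(L − 1)/2] / [L(L − 1)] = 1/2. Counting only days strictly after W, it is (L − 2)/(2L): 28/60 = 46.7% for a 30-day month, and 46.7% pooled over the calendar. If onset is uniform over the month (an assumption), about half of the affected events began on izokibep and about half on placebo.

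**Example.** First dose 24 January 2024; W = 15 May 2024. An AE recorded as starting in May 2024 is set to 1 May and counted under placebo. Of the 31 possible days, 31 − 15 + 1 = 17 are on or after the switch.

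**Step 4: the other arm.** In izokibep-first subjects the same rule moves crossover-month events that began after Week 16 back into Period 1. Treatment is unchanged, but that arm's Period 1 count can rise too.

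**The case against.** A reader might infer that the rule breaks the SAP's own conservative principle. The wording does not support that. SAP 8.3 ties the principle to whether an AE could be treatment-emergent (or a medication concomitant), and an AE set to day 01 of the crossover month is still after the first dose, so it remains treatment-emergent. The gap is in period assignment, which the principle does not address.

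A reader might also infer that the error always favours izokibep. That holds within the crossed-over group only. The rule takes no account of arm, and step 4 shows that the izokibep column of the same randomised table can also gain post-Week-16 events. The documents do not allow the net direction to be determined.

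Nor are all these events izokibep events. Those that began before the switch are placed correctly, and those that worsen in Period 2 are counted there as well.

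The consequences are also limited. Safety data carry no p-values (Protocol 9.3.5), summaries after Week 16 are exploratory (SAP 8.1), the combined tables still count the event, and the listings show original dates (SAP 9.8.2), so a partial date is visible. Visits at Weeks 16, 17 and 20, with one hour of observation after the Week 16 and 17 doses (Protocol 1.3 and 6.1.1), make an unknown start day around the switch less likely.

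All of this stands, and it limits size and direction. It does not remove the point that a stated rule can put an event that began on izokibep under placebo.

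**Conclusion.** The point holds as a minor one. For a placebo-first subject, an AE with a known month and unknown day in the crossover month goes to Period 1 for 96.7% of calendar dates and is undefined for 3.3%. In that group the placebo count can only rise and the Period 2 izokibep count can only fall. Treatment-emergent status and the total-study tables are unaffected, and no direction can be claimed for the randomised Period 1 comparison.

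The estimate that about half of the affected events began on izokibep rests on uniform onset within the month. The number of such events cannot be computed, because the documents give no count of partially dated AEs. It is probably small and could be zero.

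**What to change.** Add one branch to SAP 8.3. For subjects randomised to placebo, if the start day is missing and the month and year equal those of the first Period 2 dose, impute the start to the date of that dose, unless the end date is before it. State explicitly that such an event counts in Period 2, because SAP 6.10.2 requires a start after Period 2 dosing begins and an imputed date has no time. This also settles the case of a switch on day 01. Report the number of events reassigned.

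Leave the existing rule for the izokibep-first arm, where Week 16 does not change treatment. Do not extend the branch to starts with only the year known. SAP 8.3 already sends these to the first-dose date when the year matches, and first dose and Week 16 share a calendar year for about 69% of dates (253/365, first-dose dates spread evenly), so the two rules would conflict.

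The cost is a few lines of text and code and no new data. The downside is that some events that truly began on placebo will be counted in Period 2. The two arms will also be treated differently in the crossover month, in a direction that does not favour izokibep; the reported count of reassigned events lets a reader judge how much this matters.
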